7.3 Open Label Phase Study Visits

Optional Open Label Follow Up Phase - Visits 4 and 5 (weeks 36 and 48)

The subject will continue in the open label phase of the trial if:

- The subject has completed the 24 week randomized treatment phase
- The subject has provided consent to participate in the open label phase

The following study procedures would be performed at Visits 4 and 5:

The same study procedures that were performed at visits 1, 2 and 3 would be performed at these visits with the following exceptions:

- A pulmonary function test will be performed at **visits 5 only**.
- If HRCT was performed as standard of care, the results should be recorded at **visit 5 only**.
- The physical activity monitor, FitBit One ® will not be used in the open label phase of the trial.

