3.1.1 Study Schema

We will enroll 20 adult subjects with Syn-ILD across 5 clinical sites. We expect enrollment to be completed within 15 months. A 1:1 randomization scheme for active drug: placebo as a weekly SQ injection with their SOC for 24 weeks. All patients can then enter an optional open label follow-up after the 24-week randomized, controlled phase, during which all subjects receive 24 weeks of ABT in the same fashion as the initial study phase. This follow-up phase will assess durability, long term response and safety in patients who were in the active treatment arm while allowing the placebo arm to receive active drug, thus improving recruitment and study power.

Patient must have active ILD associated with anti-synthetase syndromes (a subset of myositis) that are being given SOC treatment for ILD. Patients could have refractory disease with flare up or new onset disease. Patient may or may not have active myositis (PM/DM). We anticipate the continued participation of all subjects in open label extension phase.

Open label phase: At the end of the active study period (week 24 closing visit), patients in either arm can enroll into the optional open-label phase of 24-week ABT therapy (125 mg SQ injection weekly).

a. **Standard of Care (SOC):** The SOC of patients with Syn-ILD includes steroids OR another IS agent OR a combination of steroid and another IS agent. Thus, we will allow steroids and/or only 1 additional IS agent. **Additional IS agent can be either mycophenolate mofetil (MMF) or azathioprine (AZA), but not both.** Patients on steroids alone can be enrolled without additional IS agent. Maximum dose allowed for MMF is 3 gms/day and for AZA is 200 mg/day. Patient should be on stable dose of MMF or AZA for 4 weeks and/or stable dose of steroids 2 weeks prior to Visit 1. Visit 1 is the time of first ABT/placebo dosing. Overall goal is to enroll patients into the trial as soon as the SOC drug has achieved stable dosing. Prednisone taper will be allowed at maximum dose of 60 mg at baseline (Visit 1), at which time a forced prednisone taper will commence as outlined below. Dose of concomitant medication cannot change throughout the phase I of the trial (24 weeks) unless safety/toxicity issues supervene.

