4.2 Exclusion Criteria

A patient will be excluded if any of the following Exclusion Criteria are met:

1. Severe end stage lung disease:
 - a. FVC $\leq 30\%$ *or* FEV1 $\leq 30\%$ *or*
 - b. Requirement of high O₂ requirement ≥ 6 L/min at rest for >1 month before the study enrollment *or*
 - c. Listed for lung transplantation *or*
 - d. PI feels that ILD is severe and end stage fibrosis is such that there is low potential for improvement with any disease modifying intervention.
2. Subjects under the age of 18.
3. Known active current or history of recurrent bacterial, viral, fungal, mycobacterial or other infections (including but not limited to tuberculosis and atypical mycobacterial disease, hepatitis B and C, and herpes zoster, but excluding fungal infections of nail beds).
4. Any major episode of infection requiring hospitalization or treatment with IV antibiotics within 4 weeks of screening.
5. Active TB requiring treatment within the previous 3 years. Patients should be screened for latent TB using PPD/or quantiferon gold within last 1 year and, if positive, treated following local practice guidelines prior to initiating ABT. Patients treated for active tuberculosis with no recurrence in 3 years are permitted.
6. Primary or secondary immunodeficiency (history of or currently active) unless related to primary disease under investigation.
7. Pregnant women or nursing (breast feeding) mothers.
8. History of alcohol, drug or chemical abuse within 1 year prior to screening or any medical condition or physical or psychological state that the PI feels would not allow the subject to safely complete the study.
9. Major surgery (including joint surgery) within 8 weeks prior to screening or planned major surgery within 6 months following randomization.
10. Treatment with any other investigational agent within 4 weeks (or 5 half-lives of the investigational drug, whichever is longer) of screening.

11. Previous treatment with the following cell-depleting therapies, including investigational agents or approved therapies: CAMPATH, anti-CD4, anti-CD5, and anti-CD3.
12. Previous treatment with ABT.
13. History of severe allergic or anaphylactic reactions to monoclonal antibodies.
14. Evidence of serious uncontrolled concomitant cardiovascular, nervous system, renal, hepatic, endocrine (include uncontrolled diabetes mellitus) or gastrointestinal disease (including complicated diverticulitis, ulcerative colitis, or Crohn's disease.)

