7.0 OBSERVATIONS PER VISIT

7.1 Screening Visit (Visit 0)

The following assessments will be performed during the Screening Visit:

Screening Visit (Visit 0)

1. Obtain informed consent from the subject.
2. Review concomitant medications for defined study washout and restriction of immunosuppressive (IS) medications.
3. Urine Pregnancy (if applicable) for all females of childbearing potential.
4. Obtain safety screening tests to include: serologies for Hepatitis B (Hep B surface Ab, surface antigen and core antibody), Hepatitis C (Qualitative HCV antibody) and tuberculosis (Quantiferon TB Gold) if a negative result was not obtained **within the last year**. If Quantiferon gold is non-interpretable or cannot be done, then skin PPD test for tuberculosis should be done.
5. Pulmonary Function Test (PFT) with DLCO should be obtained.
6. If a High-Resolution Computed Tomography (HRCT) chest has been completed as part of the patients' standard of care the results should be recorded on the HRCT chest ILD Assessment Form.
7. Brief Evaluation (history/physical)
8. Obtain and record vital sign measurements.
9. Complete screening evaluation, demographics and screening criteria assessments.

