7.2 Other Study Visits

Study Visits 1, 2 and 3 (Weeks 0, 12, and 24)

Subjects who are eligible will visit the study site and enter the randomized treatment phase after randomization. Visit 1 should take place within 21 days after the Screening Visit.

All eligible subjects will receive their first injection of either abatacept 125mg SQ injection or placebo as per randomization at Visit 1. The following assessments will be performed:

The following research procedures will be conducted at Visits 1, 2 and 3 unless otherwise noted:

- Review concomitant medications
- A urine pregnancy (if applicable) will be performed for all females with child bearing potential.
- Site pharmacist will randomize subject to receive either study drug or placebo.
- Perform and record functional test (6 minute walk distance test - 6MWD)
- Administer patient questionnaires to include: dyspnea, patient global, SF-36 and health assessment questionnaires and patient assessment of change
- Site Investigator to perform Manual Muscle Test (MMT-8)
- Site Investigator to complete MDAAT, brief physical exam and physician assessment of change
- Obtain safety screening tests to include: creatine kinase(CK), aldolase, complete blood count with differential, serum creatinine and liver function tests
- Obtain research repository blood per study schema (Appendix A)
- Instruct the subject on how and when to use the FitBit One ® device. Patient will wear FitBit device for 7 consecutive days one a month for 6 months. Refer to Manual of Operations for specific procedures for syncing the device. - **visit 1 only**
- A pulmonary function test will be performed at **visits 2 and 3 only**
- Assess and record adverse events (if applicable) – **visits 2 and 3 only**
- If a High-Resolution Computed Tomography (HRCT) chest has been completed as part of the patient standard of care, the research coordinator will obtain and record the results of this test for research purposes at **visit 1 and 3 only**. A CD of HRCT chest (at baseline and follow up) should be mailed to coordinating center for centralized evaluation in future.

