- **At visit 1 only**, you will instruct the subject on how to do the subcutaneous injection of the study drug. The subject will self-administer the study drug at Visit 1 to ensure adequate knowledge. Study drug will be dispensed to the subject at study **visits 1 and 2** (approximately 11 - 12 pre-filled syringes) to continue weekly at home. Note at study **visit 3**, that open label drug should be dispensed to the subject if continuing into the open label Phase II of the study.

Subjects will be informed that the FitBit device must be returned to the research team once they have completed the trial. The FitBit device will be then be re-assigned to future subjects at your site. The FitBit device is setup with individual accounts therefore no data from a previous participant will remain on the device. Please refer to the Manual of Operations for further guidance on setting up a de-identified account for each participant.

The following research activities will occur in between study visits 1, 2, 3 and 4:

- Approximately one week after the subject has been randomized (Visit 1) at the study center, you should call the subject to determine if the subject has experienced any adverse

- events, difficulty with administering the self-injection and to confirm steroid taper compliance. This call should be documented in your site source documentation.
- To insure that we are capturing and addressing potential side effects or deterioration in condition, the coordinators were instructed to call the subject monthly to review for adverse events, steroid taper compliance, and any signs of deterioration from the steroid taper. The call will be documented in the sites source documentation.

Unscheduled Visits: The subject should be seen for an unscheduled visit if any worsening in condition has occurred.

The following research procedures will be conducted at an unscheduled visit:

- Review concomitant medications
- Administer patient questionnaires to include: dyspnea, patient global, and health assessment questionnaires and patient assessment of change
- Site Investigator to perform Manual Muscle Test (MMT-8)
- Site Investigator to complete MDAAT, brief physical, physician global assessment exam and physician assessment of change
- A pulmonary function test (PFT) will be performed as SOC for worsening condition as deemed necessary by investigator.
- Assess and record adverse events (if applicable)

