APPENDIX B: STUDY FLOW CHART/SCHEMA

Month	0-21 days before study drug	Open Label												Unscheduled Visit
		0	1	2	3	4	5	6	7	8	9	10	11	12
(weeks)	0	+7 days from V1	8	12	16	20	24	28	32	36	40	44	48	
Visit	Screen	1	Call	Call	2	Call	Call	3	Call	Call	4	Call	Call	5
	or													
	Visit 0													
Safety Laboratory Testing														
Urine Pregnancy (if applicable)	X	X			X			X			X			X
CK, Aldolase		X			X			X			X			X
CBC, Creatinine, LFT		X			X			X			X			X
Serologies (HCV, HBV) or TB screening if not done within last 1 year	X													
Data Collection														
Screening demographics	X													
Screening evaluation	X													
Screening criteria	X													
Randomization form		X												
PFT (FVC, FEV1, DLCO)	X			X			X						X	**
HRCT chest (if done as SOC) *	X							X					X	**
HRCT ILD Assessment Form (if done as SOC)	X							X					X	
Dyspnea questionnaire		X		X			X			X			X	X
Patient Global Assessment		X		X			X			X			X	X
HAQ		X		X			X			X			X	X
MMT-8		X		X			X			X			X	X

MDAAT		X		X		X		X				X	X
Physician Global Assessment		X		X		X		X				X	X
Physician Assessment of Change				X		X		X				X	X
Patient Assessment of Change				X		X		X				X	X
SF 36 QoL Questionnaire		X		X		X		X				X	
Brief Evaluation (history/physical)	X			X		X		X				X	X
Six Minute Walk Distance (6MWD)		X		X		X		X				X	
Average daily step count on Fitbit One ® (measured for 7 days at baseline and every month for 6 months)		X		X		X							
Adverse Event/Tolerability Monitoring		X		X		X		X				X	X
Follow Up Call (assess AE's.confirm steroid taper per protocol and subjective clinical worsening)			X	X		X	X	X	X			X	
Bio-specimen Repository Collection		X		X		X		X				X	
RESEARCH SPECIMEN COLLECTION													
PAXGene tube (ml)		8		8		8		8				8	
Stored cells (ml) Green Top		16		16		16		16				16	
Stored Serum (ml) SST		16		16		16		16				16	

* An HRCT scan done as SOC within the last 6 months is required for entry into the trial to meet eligibility criteria.

** HRCT and PFT done as SOC for worsening condition as deemed necessary by investigator.

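### Open-label entry in 7.3 has no TB condition, so in the worst case a placebo patient first takes abatacept at week 24 on a TB result 533 to 554 days old (low severity)

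*Combined protocol and SAP*

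**What the plan says.** **TB screening at entry.** Section 4.2 item 5 sets the TB standard: "screened for latent TB using PPD/or quantiferon gold within last 1 year and, if positive, treated following local practice guidelines prior to initiating ABT". Section 7.1 item 4 puts the test at Visit 0 and makes it conditional: "Hepatitis C (Qualitative HCV antibody) and tuberculosis (Quantiferon TB Gold) if a negative result was not obtained" in the preceding year. The Appendix B row, "Serologies (HCV, HBV) or TB screening if not done within last 1 year", has a single mark, in the screening column.

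**After entry.** The laboratory list in 7.2 for Visits 1 to 3 reads "Obtain safety screening tests to include: creatine kinase(CK), aldolase, complete blood count with differential, serum creatinine and liver function tests". It has no TB test, and neither does the list of on-treatment evaluations in 10.2. Section 7.3 carries the Visit 1 to 3 procedures forward to Visits 4 and 5, so it adds none.

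**Open-label entry.** The two conditions in 7.3 are "The subject has completed the 24 week randomized treatment phase" and "The subject has provided consent to participate in the open label phase". At Visit 3, section 7.2 notes "that open label drug should be dispensed to the subject if continuing into the open label Phase II of the study". Section 3.1.1 says that this phase gives the placebo arm the active drug, and 4.0.1 expects every subject to continue.

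**Pre-treatment list.** Section 10.1 includes hepatitis and TB screening, if none was done in the past year, among evaluations due in the two weeks before a patient's first treatment. It names abatacept there, not study drug. Section 3.1.1, however, states "Visit 1 is the time of first ABT/placebo dosing".

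**The concern.** The TB check in 4.2 item 5 is meant to come before abatacept is started. For the abatacept arm that moment is Visit 1, close to screening. For the placebo arm it is week 24, and the schedule does not repeat the check there. Urine pregnancy testing, also on the 10.1 pre-treatment list, is repeated at Visit 3; TB is not.

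What is at stake is safety at first exposure to an immune-modulating drug, for up to 10 placebo patients. Section 6.1 lists tuberculosis among the uncommon reactions to abatacept. The blood counts, liver tests, examinations, calls and 6-month HRCT may show active disease, but none of them tests for latent TB, which is what 4.2 item 5 addresses.

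**Working it through.** The plan states no figure for the age of a TB result, so there is nothing to reproduce. The check is date arithmetic.

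**Inputs**
- Look-back for an accepted negative result: 1 year = 365 days (7.1 item 4; 4.2 item 5).
- Screening to Visit 1: 0 to 21 days (7.2).
- Visit 1 to open-label dispensing at Visit 3: 24 weeks = 24 × 7 = 168 days (3.1.1, 7.2).

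The documents do not fix whether the year is counted back from Visit 0 or Visit 1. The 0-to-21-day range covers both.

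**Maximum age of the result at first actual abatacept dose**
- Abatacept arm: 365 + (0 to 21) = 365 to 386 days.
- Placebo arm: 365 + 0 + 168 = 533 days, up to 365 + 21 + 168 = 554 days.
- Placebo arm, excess over one year: 533 − 365 = 168 days, up to 554 − 365 = 189 days.
- If the ± 2 weeks that 10.2 allows for the PFT also applies to Visit 3 (assumption), the placebo range widens to 533 − 14 = 519 and 554 + 14 = 568 days.

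**Who is not affected**
- Tested at Visit 0: the result is 168 to 168 + 21 = 189 days old at week 24, well inside one year.
- Relying on a prior result: it stays within one year at week 24 if, at Visit 0, it was at most 365 − 168 = 197 days old (no screening gap) or 365 − 168 − 21 = 176 days old (full 21-day gap). With Visit 3 two weeks late (same assumption), the limit is 176 − 14 = 162 days.

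**How many are affected.** The documents do not say how many patients will enter on a prior result, or how old those results will be. With 10 patients in the placebo arm, the count lies between 0 and 10.

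**Comparison with continuing patients.** An abatacept-arm patient's result can also be 533 to 554 days old at week 24. By week 48 it can be 365 + 21 + 48 × 7 = 365 + 21 + 336 = 722 days old. The plan accepts this, so the distinctive feature of the placebo arm is first exposure, not the age of the result alone.

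**The case against.** The strongest reply is that 10.1 already covers the case. Read literally, it counts back from first treatment with abatacept by name, and for a placebo patient that is week 24. Item 5 of 4.2 also speaks of initiating abatacept. A reader might go further and infer that the schedule breaches 10.1. The documents do not support that. The 10.1 list resembles the Visit 0 column of Appendix B, it sits with screening demographics and criteria, it yields to other specifications, and 3.1.1 treats Visit 1 as first dosing for both arms. The reading stays open. On either reading, a site following 7.2, 7.3 and Appendix B would not do the test.

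Second, one year is an entry look-back. No section requires a result less than a year old at later dosing, and continuing abatacept patients exceed it too. That stands: renewing the check at crossover is a sensible preference, not the enforcement of an existing rule.

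Third, 533 to 554 days is the extreme case and needs a result right at the edge of the look-back. That also stands.

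Fourth, the risk is small. A reader might multiply the 6.1 frequency by the 10 placebo patients to get an expected number of cases. That would count all TB in all 10. A repeat test can help only those whose older result has since turned positive, and the documents give no conversion rate. The preventable number is therefore smaller and cannot be computed here.

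Finally, active disease is not unwatched: 4.2 item 3 excludes known active infection, adverse events are reviewed at visits and monthly calls, and 9.2 lets the investigator stop treatment.

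**Conclusion.** The gap is real and of low severity. Nothing in the visit schedule or the 7.3 conditions renews TB screening before a placebo patient's first abatacept dose, and the result relied on can be 533 to 554 days old at worst. That range assumes a one-year look-back used in full, a screening interval of 0 to 21 days and nominal week-24 timing. Patients tested at Visit 0 are unaffected; otherwise the number is unknown, between 0 and 10.

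This is an inexpensive safety improvement and a clarification of 10.1, not a breach of a clear rule. The preventable TB risk is very small and not estimable from the documents, and the primary analysis of FVC at week 24 is not affected.

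**What to change.** Add one entry condition to 7.3: *a negative TB result no more than 1 year old, or documented treatment of latent TB, is on file before open-label drug is dispensed.* Apply it in both arms by the age of the result, so that it reveals nothing about allocation.

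**Preferred way to meet it: at Visit 0.** Narrow the waiver in 7.1 item 4 and Appendix B so that a prior negative result is accepted only if it is at most 176 days old (162 days if Visit 3 may run two weeks late, an assumption). Otherwise test at Visit 0. No testing is then needed during the blinded phase.

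**Alternative.** Repeat the test shortly before open-label dispensing, only in patients whose result will be over 1 year old by then. Hold open-label drug until any positive has been evaluated and treated under local guidelines. A mid-study test, for example at week 12, is better avoided: a positive could interrupt or confound blinded treatment before the primary endpoint, with only 10 patients per arm.

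**Cost.** One line in 7.3, plus an edit to 7.1 and Appendix B. The test and its skin-test fallback are already in the protocol. Expect a few additional TB tests (at most one for each of the 20 enrolled patients). Under the alternative, open-label dosing may be delayed for a short time in a patient who newly tests positive.

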8.0 DOSE MODIFICATION/TOXICITY MANAGEMENT

A number of measures will be taken to ensure the safety of patients participating in this study. These measures will be addressed through exclusion criteria (see Section 4.2) and routine monitoring as follows.

Patients enrolled in this study will be evaluated clinically and with standard laboratory tests before and during their participation in this study. Safety evaluations will consist of medical interviews, recording of adverse events, physical examinations, blood pressure, and laboratory measurements. Subjects will be evaluated for adverse events (all grades), serious adverse events, and adverse events requiring study drug interruption or discontinuation at each study visit for the duration of their participation in the study.

9.0 CRITERIA FOR SUBJECT DISCONTINUATION

9.1 Abatacept-Specific Criteria

Subjects who meet the following criteria should be discontinued from the study:

- Anaphylaxis or hypersensitivity reaction or requires an interruption of the study drug because of symptoms of anaphylaxis or hypersensitivity (ABT should be permanently discontinued from these patients)
- If, following initiation of study drug, it is subsequently discovered that a study participant is pregnant or may have been pregnant at the time of study drug administration, including at least 5 half-lives administration, the study drug will be permanently discontinued.

9.2 General Criteria

- Inability of subject to comply with study requirements

Determination by the investigator that it is no longer safe for the subject to continue therapy

10.0 CLINICAL AND LABORATORY EVALUATIONS

Refer to Appendix B.

10.1 Pre-Treatment Evaluations

Unless otherwise specified, the following evaluations must be performed within two weeks prior to the date of each patient's initial treatment with Abatacept:

- Urine Pregnancy (if applicable)
- Serologies (HCV, HBV) or TB screening if not done within last 1 year
- Screening demographics, evaluation, and criteria
- PFT (FVC, FEV1, DLCO)
- HRCT chest (SOC)

Brief Evaluation (history/physical)

10.2 Evaluations During Treatment

- PFT (FVC, FEV1, diffusing capacity of the lungs for carbon monoxide (DLCO)) will be evaluated at baseline (accepted if within prior 1 month of screening visit), 3, 6 months (+/- 2 weeks). If patient opts into the open label phase, then additional PFT at 12 months will be done.
- HRCT chest at baseline i.e. visit 0/1 (accepted within 3 months of screening visit if no significant change in clinical status has occurred in 3 months) will be done as standard of care (SOC) in clinical practice. HRCT chest at 6 month (+/- 1 month) follow up i.e visit 3 will be done as SOC as well. In patients opting for open label phase, additional HRCT at 12 months (+/- 1 month) follow up i.e visit 5 will be collected if done as SOC.

- Muscle enzyme: creatine kinase (CK) and aldolase levels at baseline, 3, 6 months. If open label phase – then additional 9 and 12 months will be obtained.
- Safety monitoring labs – complete blood count (CBC), liver function test (LFT), serum creatinine will be done at baseline, 3 and 6 months. If patient opts for open label phase, these safety labs will also be done at 9 and 12 months.
- Research specimens (serum, cells, etc) collected at each study visit for future experimental studies.

Refer to study schema in Appendix B

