3.3.1 Primary Outcome Measures

The primary outcome criteria for efficacy will be the FVC% change from the baseline visit to week 24 between the 2 treatment arms (SOC/placebo vs. SOC/ABT). An intention to treat analysis will be used. Ranked ANCOVA will be used with average standardized rank change in the predicted FVC% as the outcome measure and the standardized rank baseline as a covariate. Primary outcome criteria for safety and tolerability will be adverse events (routine adverse events or tolerability issues and serious adverse event) between the 2 treatment arms (SOC/placebo vs. SOC/ABT). Chi-square (or Fischer exact test) and t-test (or Mann-Whitney) will be used based on data variable and distribution.

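### The plan does not say which lung function test is the baseline for the primary FVC% endpoint, and it allows one taken up to about 51 days before the first dose

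*Combined protocol and SAP*

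**What the plan says.** Section 3.3.1 defines the endpoint: "The primary outcome criteria for efficacy will be the FVC% change from the baseline visit to week 24". The other provisions that bear on the baseline are these.

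- **Section 10.1** lists PFT among pre-treatment tests that "must be performed within two weeks prior to the date of each patient's initial treatment with Abatacept". The sentence opens with a proviso giving way to anything specified elsewhere.
- **Section 7.1** says of Visit 0: "Pulmonary Function Test (PFT) with DLCO should be obtained". **Section 7.2** adds: "Visit 1 should take place within 21 days after the Screening Visit". **Appendix B** marks the PFT in the column headed "0-21 days before study drug".
- **Section 10.2** says of the baseline PFT: "accepted if within prior 1 month of screening visit".
- **Section 7.2** restricts PFTs in the randomised phase to Visits 2 and 3. Section 3.1.1 identifies Visit 1 as the time of first dosing, so no PFT is taken then.
- **Section 4.1** also accepts a PFT from the last 3 months, but only to decide eligibility. It is not a baseline window.

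Sections 3.1.1 and 4.1 require mycophenolate or azathioprine to be stable for 4 weeks before Visit 1, and steroids for 2 weeks.

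**The concern.** A patient may have both a recent clinical PFT and a Visit 0 PFT. Nothing says which one enters the primary analysis, so two sites could each follow the protocol and compute different endpoints for the same patient.

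The population makes an old value risky. Active ILD, as defined in section 3.1.1, means onset within 3 months or worsening that led to a treatment change within 3 months. Section 4.1 aims to start trial drug soon after background therapy begins. Lung function may be moving in either direction in the weeks before Visit 1, and a change measured from an early PFT includes that movement.

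Three things are affected: the variance of the primary outcome with 10 patients per arm; the effect sizes for drug and placebo that section 12.1 wants for planning a later trial; and the secondary endpoints with fixed FVC thresholds (progression, improvement of at least 10%, treatment failure).

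**Working it through.** **The plan's own power figure.** Section 12.1 states more than 90% power for a mean change of −10 on standard of care against +5 on abatacept, a difference of 15, with 10 per arm. It gives no SD, alpha or sidedness, so the figure can be neither reproduced nor refuted. At two-sided alpha 0.05 (assumed), 90% power needs an SD of change of at most 10.35 (normal approximation) or 9.78 (t test).

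**Longest lag.** Taking a month as 30 days: 30 (section 10.2) + 21 (section 7.2) = 51 days before first dose, or 52 with a 31-day month. The treatment period is 24 × 7 = 168 days, so 51/168 = 30%. The measured change can span 168 + 51 = 219 days.

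**Relation to background therapy.** 51 − 28 = 23 days, so the oldest permitted PFT can precede stable mycophenolate or azathioprine by about 3 weeks. A Visit 0 PFT, at most 21 days old, falls inside the 28-day stable period.

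**Pre-dose change.** Assume the section 12.1 decline of 10 points over 24 weeks is linear and also applied before dosing. Pre-dose change = 10 × lag/168:

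- 14 days: 0.8 points
- 21 days: 1.25 points
- 51 days: 3.0 points, the maximum for one patient
- lags uniform on 0 to 51 days, mean 25.5: 1.5 points on average

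**Bias.** The lag is fixed before randomised treatment starts, so its effect is equal in expectation in both arms. In simulation with a mean pre-dose drift of −3, the arm difference stayed at 15.0, and type I error was 5.3% under the null. The within-arm mean on standard of care moved from −10 to −13 (all patients at a 3-point drift). A drift identical in every patient cost essentially no power (86.5% without, 86.2% with, SD 9.8).

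**Noise.** Power is lost only if pre-dose change differs between patients. If each patient's slope persists, the slope part of the measured change is multiplied by (168 + lag)/168: 189/168 = 1.125 at 21 days and 219/168 = 1.304 at 51 days.

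The simulation used rank ANCOVA with 10 per arm, mean slope −10 per 24 weeks, measurement SD 3 and uniform lags. The slope SDs and measurement SD are assumptions.

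| Slope SD | Arm difference | Power, lag 0–21 days | Power, lag 0–51 days |
|---|---|---|---|
| 6 | 10 | 74% | 70% |
| 10 | 15 | 75% | 70% |
| 8 | 15 | 88.5% | 84% |
| 6 | 15 | 97% | 96% |

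The loss is about 1.5 to 5 points. Separate runs differ by about a point: one repeat of the second row gave 75.0% against 69.3%, and one repeat of the fourth gave 97.4% against 95.8%. Section 12.1 plans on a difference of 15; the row with 10 shows a smaller effect.

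**Partial use of the allowance.** If 30% of patients (assumed) had lags of 0 to 51 days and the rest 0 to 21, power was 73.1% in each of the first two settings, about 2 points below the 21-day figure.

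**The case against.** The strongest reply is that the sections can be read together. The section 10.1 rule yields to more specific provisions, and section 10.2 is the specific provision for PFT. The 21 days in section 7.2 governs visit spacing, and section 10.2 counts back from screening, so the two do not collide. Visit 0 already has a scheduled PFT. A 51-day baseline needs three things at once: a site using the allowance, a PFT a full month old, and Visit 1 on the last permitted day. In a 20-patient proof-of-concept trial, accepting a recent clinical test spares a repeat and is a defensible feasibility choice.

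Much of this stands. A reader might infer that the plan contains three flatly contradictory windows; the proviso in section 10.1 does not support that. What survives is that no section says section 10.2 is the exception or names the baseline when two PFTs exist, and that the allowance itself is long for recently active disease.

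A reader might also set a 14-day limit against 51 days and report a loss of 6 or 7 points (76.3% to 70.3%, and 76.5% to 69.3%, in the first two settings). That comparison overstates what can be recovered, because a Visit 0 PFT may itself be 21 days old.

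**Conclusion.** The point holds as a gap in the definition of the primary endpoint, together with a baseline that may be about 51 days old. It is a cheap improvement and does not threaten the validity of the trial.

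A reader might infer that pre-dose change biases the treatment comparison. It does not: the expected contribution is the same in both arms. Nor is 3 points a typical contamination; it is the maximum for one patient under a linear trend, and about 1.5 points is the average if lags were uniform up to 51 days.

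The harm is extra variance, within-arm changes that do not describe the treatment period, and threshold endpoints reached partly before dosing. A 3-point pre-dose fall would be 3/10 of the way to a 10-point decline. The power cost of about 1.5 to 5 points rests on assumed slope SDs of 6 to 10, a measurement SD of 3, slopes that persist through dosing, and every patient's lag being uniform up to 51 days. The documents supply none of these, nor how often the allowance would be used; infrequent use makes the cost smaller.

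**What to change.** - In section 10.2, define the endpoint baseline as the PFT done at Visit 0, already scheduled in section 7.1 and Appendix B, and remove the one-month allowance for that purpose.
- Keep older PFTs for eligibility only, as section 4.1 already does.
- Make section 10.1 state the same maximum interval from PFT to Visit 1 as section 7.2 and Appendix B.

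The cost is protocol wording, plus a repeat test at Visit 0 for a few patients who have a recent clinical PFT. A lag of up to 21 days remains, which at the assumed rate is at most 1.25 points. A PFT that old can still precede the 2-week steroid stability period by 21 − 14 = 7 days.
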